Step 3. Review with YAB. Drs. [name] and [name] will facilitate the review of the mLab App user interface, content, and function with the YAB. Through our review, we will ensure that the mLab App is culturally appropriate for both YMSM and YTGW. [name] will insert changes directly into the mLab App mock-ups viewed on a screen, supplemented by note-taking by study staff and audio-recorded. This allows us to confirm meaning, make revisions as necessary, and reach consensus with the YAB. [name] will probe for further discussion on feasible ways forward and to ensure that the mLab App meets the current prevention guidelines. We will incorporate the recommended changes. As a final step, we will have members of the YAB test the final mLab App after the meeting in their own settings (e.g., Home) and return any comments or additional edits within 2 weeks. Final recommendations for the user interface will be shared with [name], who will work with his team and the graphic design team at Little Green Software (see letter of support) to make the final updates to the app.

Aim 2: Evaluate the efficacy of the mLab App in improving both HIV testing rates and linkage to care versus standard preventive care in 525 Black, Latino and other young men and transgender women (inclusive of YMSM and YTGW age 18-29 years) in a 12-month multi-site trial, with randomization at each site to three groups arm 1: intervention (mLab App) (N=210); arm 2: standard of care HIV information control arm (N=210); arm 3: OraQuick home test kits only (N=105).

Hypothesis 1. Youth randomized to the mLab App arm, as compared to youth in the standard of care HIV information control arm, will have: a) increased rates of HIV testing within the first 6 months of the trial; and b) increased rates of re-testing in months 7-12 of the trial.

Hypothesis 2. The total number of youth who test HIV positive and link to care in the mLab App arm will be greater as compared to the standard of care HIV information control arm.

Hypothesis 3. The image processing in the mLab App will: 1) have no statistically significant difference in sensitivity or specificity when compared to confirmatory testing, 2) have greater sensitivity and specificity when compared to the user-submitted self-analyses.

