Arm 1-Intervention Arm (mLab App + HIV home test). Youth randomized to the intervention arm will be provided with the mLab App, 2 OraQuick tests (including the package insert), and a box of condoms to take home at baseline. They will receive 2 more OraQuick tests at their 6 month visit. Participants may come in person to receive their tests or their tests may be mailed to them at their verified address if they are unable to complete the in-person visit. The OraQuick tests will be sent via tracked shipping through USPS, FedEx, and UPS. At their baseline appointment, youth will also be sent an email or text with links to mobile-optimized online prevention information, including PrEP and HIV testing information that is found on the CDC website. They will also receive a study information card listing the Columbia University School of Nursing / Lurie Children's study teams' contact information. The goal of the mLab App is not for partner testing. We will advise participants upon study enrollment and consent (see Protection of Human Subjects) that the technology is NOT to be used for this purpose in this study. Given this limitation, we will suggest that participants who have partners who are interested in testing should contact the study team in each respective city for more information on HIV testing. We will also reinforce with participants that the mLab App is considered a screening device and they should seek confirmatory testing (for both negative and positive test results). The mLab App is mobile app on your phone that is accessible using a login name and password. The app will provide HIV prevention information, push notification reminders for testing, step-by-step instructions for using the OraQuick HIV tests, an image upload function to send an image of your OraQuick HIV test to the study team.

Participants will:

- a) be asked to manually enter the Oraquick test results; and
- b) take a picture of the test results for the app to analyze the results; and

- c) receive the app's interpretation of the Oraquick test results.

By using the app, we are asking participants to help test the app's ability to interpret the results of the OraQuick tests. If you test HIV positive by the OraQuick HIV test and/or the mLab app will provide information on how to set up follow-up confirmatory testing within the following 24 hours. All information that you provide within the app will be stored on a secured server at Vanderbilt University

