Reminder notifications. Participants in the intervention arm will be instructed to use the mLab App and the HIV self-test kit at 3 months, 6 months, 9 months, and 12 months after enrollment. Participants will receive a reminder push notification 2 weeks prior to their scheduled test date and 1 week after their scheduled test date.¹³⁸ In the mLab app, if a participant indicates they have received a preliminary positive HIV test using the home HIV test, participants will be directed to another screen on their smartphone directing them to call the study team or the warm line at the NYP or Lurie clinic (depending on geographic location) to receive follow-up confirmatory testing [and if needed, linkage to care]. Participants will be told that this result does not necessarily indicate that they are HIV positive (see false positive in Protection of Human Subjects), that further follow-up testing is needed, and they should contact the clinic or the study team within 24 hours. The mLab team will return the call within normal business hours. The number and nature of calls from participants to the study team (e.g., related to mLab App use, test interpretation, distress at reactive results) will all be recorded and will be reviewed yearly or at a date determined by the DSMB with our DSMB (see letters of support). We will track linkage to follow-up testing and care. Our DSMB will carefully monitor our study activities and data – see Data Safety and Monitoring Plan. **Sound Retention Efforts.** Participants will be asked after study screening what would be the best way for us to remind them of the appointment (voice phone, text, e-mail). Participant retention during the intervention will be enhanced in several ways. First, participants will be compensated for their time to complete the baseline assessment and completing the follow-up assessments. In addition, during the follow-up survey (6 months), participants will be asked to update their locator information. Using these extensive procedures promotes participant attendance at the follow-up visits, which has been shown to be successful in previous trials.^{139, 140} **We have 4 levels of outcomes:** primary, secondary, intermediate, and program evaluation. The survey items are included in the Qualtrics attachment. The primary outcome for Aim 2 / study trial (Uptake of rapid HIV

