mLab Image-Processing Evaluation Methods. During use of the mLab App, participants will submit images of their Oraquick self-test to the app for analysis by an automated image-processing algorithm. Prior to submitting this image for analysis, participants will be asked to interpret the results of the test using the instructions that are provided standard with the OraQuick test. This self-reported result will be recorded and uploaded with the user-submitted image of their rapid test. Study team members with expertise in rapid test use and analysis will evaluate the uploaded images of each rapid test, and provide an additional assessment. The user-submitted result and the study team assessment will not be used by mLab in its automated image-processing. All users that submit tests that are identified as positive, either by the automated image-processing in mLab, the study team personnel's inspection of the image of the rapid test, or by the study participant themselves, will be referred for confirmatory testing.

(*Hypothesis 3*).**mLab Image-Processing Data Analysis Plan.** Including the confirmatory test, which will be treated as the gold standard to determine whether a test result is truly false or positive, there will be results from four analysis methods collected on the same set of tests (1. User-submitted results, 2. Study team interpretation of uploaded images, 3. Automated mLab App results, 4. Confirmatory testing). The sensitivity and specificity for each of these methods will be compared using McNemar's test. This will result in the following statistical comparisons for both sensitivity and specificity: 1) user-submitted analysis to study team analysis, 2) user-submitted analysis to mLab analysis, 3) study team analysis of uploaded images, 4) user-submitted analysis to confirmatory testing, 5) study team analysis to confirmatory testing, 6) mLab analysis to confirmatory testing.

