We will analyze difference in the aggregated data by demographic group (age, race, and risk level) to allow us to better understand engagement with the intervention and potential facilitators and barriers to mLab App use. We will evaluate if grouping by HIV status affects these results in any way (e.g., do HIV+ users engage with features differently than HIV- users?). Finally, as a web application, there is potential for slightly varied experiences on different devices or web browsers, and we will evaluate if there are differences in mLab paradata across devices and browsers.

Risks, Benefits & Monitoring

Potential Risks

The risks of participating in this study are:

We will discuss each of these risks below and describe the protection against these risks under “Adequacy of Protection Against Risks.”

General Risks:

1. A risk of taking part in this study is the possibility of a loss of confidentiality or privacy, including that associated with the app on the participants' phone. Loss of privacy means having their personal information shared with individuals outside of the study team who were not supposed to see or know about their information. The study team plans to protect the privacy of participants. Their plans for keeping your information private are described in the Privacy section of Protection Against Risk.

Risks Specific to the Use of OraQuick:

1. **Subjects must follow package instructions on the OraQuick test and always read the test results from the OraQuick test themselves given that the accuracy of the mLab application has not been proven.** Confirmatory HIV testing is still needed.
2. Participants may mistakenly believe that a negative result of the OraQuick Test means that they are not infected with HIV. There is a chance that the test does not detect an HIV infection. To offset this risk, participants will be repeatedly told that a negative result in the OraQuick test does not mean that they are not HIV infected, since infections that occurred within the prior three months may not be detected by the test, and that condoms should still be worn to avoid the risk of HIV and other STIs.

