- 5) Window Period for Interpretation of Results: In the mLab App, we have added in 2 points of instruction related to the 20-40 minute window period for the Oraquick results – see Appendix L, slides 7 and 11. Second the images will be time stamped and we will not return algorithm results if the time from reporting in screen 7 and the time to take a picture in screen 11 has been less than 20 minutes or more than 40 minutes.
- 6) Invalid Test Results: If the participant reports an invalid result – the software will send the following message back to the study participant: You reported that your results are invalid. An Invalid test result means that there was a problem running the test, either related to the specimen or to the Test Device. An Invalid test will not be interpreted by the mLab App. Repeat the test with a new Divided Pouch and a new oral fluid. Please contact the study team if you are unable to get a valid test result upon repeat testing. If the participant reports an invalid test then we will turn off the ability for the mLab App to return the algorithm results to the participants. However, invalid images will still be stored in REDCap and reviewed by the study team.
- 7) Imaging Algorithm: The parameter values in the mLab App's image processing algorithm have been validated and selected to primarily optimize sensitivity and specificity. However, it is possible for the mLab App to return both false positives and false negatives. The study team will monitor the images that are sent using the mLab App, and will contact study participants in the event of either: 1) the mLab App returns an incorrect result, and 2) a discrepancy between the participant's manually reported result and the mLab App result.

c. Additional Planned Procedures for Protecting Against/Minimizing Potential Risk/Additional Protections for Children

Procedures in the Event of a Reactive HIV Test

In the event a participant has a reactive HIV test, study team members will counsel the participant regarding the meaning of his result. Specifically, the study team will reiterate with the participant that:

- 1) His result is a preliminary positive and it is likely that he is infected with HIV;
- 2) The preliminary positive result needs to be verified with confirmatory testing;
- 3) He needs to return for the results of his confirmatory testing; and
- 4) Resources for counseling and referral to care are available to him.

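### Hypothesis 3 does not say which of a participant's strips enter the app-versus-user comparison, so user reads made after a positive is already known can be counted

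*Combined protocol and SAP*

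**What the plan says.** Hypothesis 3 part 2 (Study Aims, and again under Aim 2) is that the app will "have greater sensitivity and specificity when compared to the user-submitted self-analyses".

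- **Several strips per person.** Under Reminder notifications, arm 1 participants are instructed to test "at 3 months, 6 months, 9 months, and 12 months after enrollment". The Arm 1 section supplies two kits at baseline and two at month 6, with no condition on earlier results.
- **What is compared.** In the mLab Image-Processing Evaluation Methods, study staff "will evaluate the uploaded images of each rapid test, and provide an additional assessment". The Data Analysis Plan that follows states that "there will be results from four analysis methods collected on the same set of tests", with McNemar's test for sensitivity and specificity. It contains no first-strip restriction and no cut-off at a positive.
- **Order within a strip.** "Prior to submitting this image for analysis, participants will be asked to interpret the results of the test".
- **Feedback.** The Arm 1 section says participants will "receive the app's interpretation of the Oraquick test results". Protections against Risks, item 7, has staff contact participants when the app's result is incorrect and when there is "a discrepancy between the participant's manually reported result and the mLab App result".
- **App use by positive participants.** The Aim 3 analysis asks: "do HIV+ users engage with features differently than HIV- users".

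**The concern.** A fair comparison of two readers needs each to call the strip without knowing the reference result. Reading before upload protects a user's call from the app's output on that same strip. It does not protect the call on a second, third or fourth strip from what the user learned from earlier ones.

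The clearest problem is a participant already told that they are positive. That person is likely to enter a positive result however faint the line, so the entry reports known status and does not test reading skill. Such strips raise apparent user sensitivity and shrink the difference that Hypothesis 3 part 2 looks for. A real advantage of the app could be understated.

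A second, less certain problem is that later reads may be shaped by earlier app readings or staff contact. Because the analysis set is undefined, the choice of strips would also be left until the data are in hand.

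**Working it through.** The documents give no accuracy, sample-size or power figure for Hypothesis 3, so there is no stated figure to reproduce. The numbers below are illustrations.

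**Room for later reads.** Arm 1 has 210 participants (sample size section) and four scheduled tests, so at most 210 × 4 = 840 strips. First strips number at most 210, leaving up to 630 later ones. These are ceilings: strips reported invalid are not interpreted by the app and drop out of the app-user comparison.

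**Share of positive strips read with status known.** Assume first positives fall evenly over the four scheduled tests. Then 3, 2, 1 or 0 scheduled strips follow, a mean of (3 + 2 + 1 + 0)/4 = 1.5. If a fraction c of these are actually used, the share is f = 1.5c / (1 + 1.5c).

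**Measured user sensitivity.** Assume 80% on unprompted reads and 100% on reads with status known. Then measured sensitivity = (1 − f) × 80% + f × 100%. The last column assumes an app sensitivity of 95%, so the unbiased difference is 15 points.

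| c (assumed) | f | Measured user sensitivity | App minus user |
|---|---|---|---|
| 0 | 0% | 80.0% | 15.0 points |
| 5% | 0.075/1.075 = 7% | 81.4% | 13.6 points |
| 20% | 0.3/1.3 = 23% | 84.6% | 10.4 points |

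**What can be tested at all.** The Data Analysis section expects about 25 to 40 positive tests and does not say in which arms. If they divide by arm size, arm 1 has 25 × 210/525 = 10 to 40 × 210/525 = 16. With a two-sided exact McNemar test at 0.05, five discordant pairs all in one direction give p = 2 × 0.5⁵ = 0.0625 and six give 2 × 0.5⁶ = 0.031, so at least six are needed.

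With one positive strip per person, 80% against 95% and independent errors, the probability that the app is right and the user wrong is 0.95 × 0.20 = 0.19. The reverse is 0.05 × 0.80 = 0.04. With 16 people that is about 3.0 and 0.6 expected discordant pairs. Exact power is about 0.4% with 10 people and 4% with 16. If all 40 positives were in arm 1, it would be about 39%.

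**The case against.** The strongest reply is that the plan does not describe diagnosed participants going on testing. Study Aims and Theoretical Framework both tie repeat-testing messages to a non-reactive result, and linkage to confirmatory testing and treatment to a reactive one. The Benefits section refers reactive arm 1 participants to services at the time of the reactive result. The Aim 3 question about HIV-positive users concerns engagement with app features, which include contact and information pages, and need not mean further strips. This stands. Such strips are possible, not stated, and may be few.

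Four stronger readings are tempting, and the documents do not support them.

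- **That the plan keeps every uploaded strip.** This would be an inference from silence. The quoted words do not define the set. Moreover, only strips flagged positive are referred for confirmation, so the set with all four results may be much smaller than all uploads.
- **That most of the app's advantage would vanish.** With c = 100% the formulas give 1.5/2.5 = 60%, a measured user sensitivity of 92% and a difference of 3 points. That requires every diagnosed participant to complete every remaining scheduled self-test, which nothing in the plan indicates.
- **That feedback pulls users toward the app.** The risk sections call the manual read the result of record and more reliable than the app, and staff contact after an app error could teach distrust. The direction is unknown. The Background description of the app also says participants will not see its interpretation. That conflicts with the Arm 1 section and with Protections against Risks, items 5 and 6, which set out when results are withheld and so presuppose that they are otherwise returned.
- **That restricting the strips would make a sensitivity advantage detectable.** The power figures above show it would not.

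It can also be said that app performance is a secondary goal, and that reads with status known work against the app and would not manufacture superiority. Both are true and limit the weight of the point. Neither is a reason to leave the analysis set undefined.

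**Conclusion.** The point holds as a gap in the definition of the analysis set. Nothing in the Hypothesis 3 plan excludes user reads made after the participant's positive status is known, and such reads bias user sensitivity upward and the app-user difference downward. Later reads that follow app feedback or staff contact are also admitted, with an effect of unknown direction.

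The size cannot be derived from the documents. It runs from nothing, if no diagnosed participant retests, to a measured user sensitivity of about 85% instead of 80% if 23% of positive strips are read with status known. That range rests on assumed values: 80% unprompted sensitivity, 100% once status is known, first positives spread evenly over the schedule, and up to one in five later scheduled strips used. The plan's linkage text suggests that the lower part of the range is more plausible.

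This is an inexpensive improvement to a secondary analysis. It does not touch Hypothesis 1.

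**What to change.** Add to the mLab Image-Processing Data Analysis Plan, for Hypothesis 3 part 2:

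1. The main set is each participant's strips up to and including the first one called reactive by any reader or confirmed positive.
2. Strips uploaded after confirmatory testing has ruled out infection may re-enter for specificity.
3. All other later strips are reported separately.
4. A supporting analysis uses each participant's first uploaded strip only, because the main set still contains later reads made after earlier app feedback.
5. Sensitivity comparisons are descriptive, given the small number of positives.

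Separately, reconcile the Background statement that participants will not see the app's interpretation with the Arm 1 section and Protections against Risks, which say or imply that they do.

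The cost is SAP wording. Uploads are already time-stamped and test results and linkage to follow-up testing are already tracked; the date of each confirmatory result must be kept with them. The downside is fewer strips and slightly less precision, mainly through losing repeat reads from people whose status is already known.
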